1.2.2.2 Pharmacokinetic Analysis of C1 Esterase Inhibitor [Human] Liquid for Injection

In Study SHP616-103, new bioanalytical assays were developed and validated for the quantitative determination of C1 INH protein and functional binding of C1 INH in human plasma. These assays differed from those used in previous Cinryze SC studies to determine plasma concentrations of C1 INH antigen and functional C1 INH activity.

Following SC administration of 1000 IU and 2000 IU C1 esterase inhibitor [human] liquid for injection, injected C1 INH was slowly absorbed with median t_{max} ranging from 36–48 hours for both C1 INH antigen and functional C1 INH binding. Mean baseline-corrected C_{max} and AUC_{last} PK parameters for both C1 INH antigen and functional C1 INH binding after IV and SC administration are shown in [Figure 5](#) and [Figure 6](#), respectively.

Figure 5 Individual and Mean (\pm SD) Baseline-corrected C_{max} Across Treatments for C1 INH Antigen and Functional C1 INH Binding (Study SHP616-103)

[figure not shown]
[figure not shown]

Figure 6 Individual and Mean (\pm SD) Baseline-corrected AUC_{last} Across Treatments for C1 INH Antigen and Functional C1 INH Binding (Study SHP616-103)

Subcutaneous administration of C1 esterase inhibitor [human] liquid for injection was less than dose proportional, with a 2-fold increase in dose resulting in 1.76- and 1.58-fold increase in C_{max} and AUC_{last} respectively for C1 INH antigen, and 0.99- and 1.09-fold increase in C_{max} and AUC_{last} respectively for functional C1 INH binding.

The baseline-corrected point estimates of the AUC_{last} ratios and 90% confidence intervals for C1 INH antigen and functional C1 INH binding was used to determine the relative bioavailability of 1000 and 2000 IU C1 esterase inhibitor [human] liquid for injection with 1000 U IV CINRYZE. The relative bioavailabilities for the 1000 IU and 2000 IU SC dose of C1 esterase inhibitor [human] liquid for injection were approximately 69% (44–110%) and 60% (38–95%) respectively for C1 INH antigen, and 67% (34–130%) and 39% (20–77%) respectively for C1 INH functional binding (in non-HAE subjects).

1.2.2.3 Dose Selection

The approach for preventative therapy in HAE patients is to provide enough CINRYZE to achieve or exceed a threshold C1 INH functional activity concentration in plasma that has a >70%

likelihood of preventing an angioedema attack. The combined data from prior SC CINRYZE studies (including the evaluation of bioavailability) along with the demonstration of similar bioavailability achieved in the completed Phase 1 single dose study of C1 esterase inhibitor [human] liquid for injection, support dose selection of 2000 IU C1 esterase inhibitor [human] liquid for injection for further evaluation in a Phase 3 study.

2. STUDY OBJECTIVES AND PURPOSE

2.1 Rationale for the Study

The sponsor has developed a new, ready-to-use liquid formulation of CINRYZE (C1 esterase inhibitor [human]). The CINRYZE liquid product (C1 esterase inhibitor [human] liquid for injection) is intended for the same indication as the licensed, lyophilized powder formulation of CINRYZE: routine prophylaxis against angioedema attacks in adolescent and adult patients with HAE. The route of administration will be SC injection, and the dosing regimen will be 2000 IU every 3 or 4 days. Shire ViroPharma anticipates that patients will benefit from the inherent advantages of SC administration, as well as the ready-to-use liquid, lower volume product compared with one requiring reconstitution. In addition, the CINRYZE liquid product is more concentrated than the licensed CINRYZE product (500 vs 100 U/mL), which should enable more rapid administration of the drug and may improve tolerability, without an expected change or compromise in efficacy.

The sponsor has selected 2000 IU of C1 esterase inhibitor [human] liquid for injection as the appropriate active dose for this Phase 3 study. This dose is based on the results of a recently completed Phase 2, randomized, double-blind, dose-ranging, crossover study that evaluated SC administration of CINRYZE with rHuPH20 (a dispersing agent) for the prevention of angioedema attacks in adolescents and adults with HAE (Study 0624-206). Results revealed greater clinical benefit with 2000 U of CINRYZE compared with 1000 U. In addition, the 2000 IU dose is supported by PK results from Study 0624-206, by the results of population PK and exposure-response modeling, and by PK data from a Phase 1 study (0624-102) that demonstrated the minimal influence of rHuPH20 on functional C1 INH activity when co-administered with CINRYZE (Section 1.2.2.1). Finally, the 2000 IU dose is further supported by the PK and bioavailability data from the Phase 1 study of C1 esterase inhibitor [human] liquid for injection (Protocol SHP616-103).

The study design was chosen as the best way to jointly address the protocol objectives of establishing efficacy (relative to placebo) and safety (ie, adequate numbers of subjects for precision of estimation in detecting potential safety signals). Additionally, this design maximizes the number of patients exposed to C1 esterase inhibitor [human] liquid for injection and minimizes patient exposure to placebo while having adequate patient exposure to placebo to assess efficacy. Thus, the proposed study is described as a “partial” crossover because 2 treatment sequences involve crossing over to the other experimental agent and the third sequence does not. All subjects will receive active treatment during this study and will have an overall two-thirds probability to be randomized to active drug in any treatment period.

2.2 Study Objectives

2.2.1 Primary Objectives

The primary objective of this study is to demonstrate superior efficacy of SC administration of 2000 IU C1 esterase inhibitor [human] liquid for injection for the prevention of angioedema attacks relative to placebo based on the normalized number of attacks (NNA) during a treatment period.

2.2.2 Secondary Objectives

The key secondary objectives are to demonstrate the superior efficacy of SC administration of 2000 IU C1 esterase inhibitor [human] liquid for injection for the prevention of angioedema attacks relative to placebo as measured by:

1. The proportion of subjects meeting the criterion of at least a 50% reduction in the NNA during the 2000 IU C1 esterase inhibitor [human] liquid for injection treatment period relative to the placebo period.
2. The NNA during each treatment period excluding the first 2 weeks.
3. The proportion of subjects meeting the criterion of at least a 50% reduction in the NNA for the 2000 IU C1 esterase inhibitor [human] liquid for injection treatment period relative to the placebo period excluding the first 2 weeks of each treatment period.

Other secondary objectives are:

- To assess the proportion of responders during treatment with 2000 IU C1 esterase inhibitor [human] liquid for injection relative to treatment with placebo, where the proportion of responders is defined as achieving at least a 50% reduction in the NNA during a treatment period relative to the pretreatment assessment (ie, the subject's attack rate without prophylactic treatment)
- To assess the severity of angioedema attacks during treatment with 2000 IU C1 esterase inhibitor [human] liquid for injection relative to treatment with placebo
- To assess the number of attack-free days during treatment with 2000 IU C1 esterase inhibitor [human] liquid for injection relative to treatment with placebo
- To assess the number of angioedema attacks requiring acute treatment during treatment with 2000 IU C1 esterase inhibitor [human] liquid for injection relative to treatment with placebo
- To assess the safety and tolerability of SC administration of 2000 IU C1 esterase inhibitor [human] liquid for injection
- To assess the immunogenicity of SC administration of 2000 IU C1 esterase inhibitor [human] liquid for injection
- To characterize the PK and PD of SC administration of 2000 IU C1 esterase inhibitor [human] liquid for injection
- To assess the clinical response and safety/tolerability of icatibant (Firazyr[®]) for the treatment of acute angioedema attacks (applicable for subjects ≥ 18 years of age)

- To assess disease activity as measured by the Angioedema Activity Score (AAS)
- To evaluate subject experience with self-administration of SC 2000 IU C1 esterase inhibitor [human] liquid for injection
- To evaluate the impact of treatment on health status (quality of life) in this patient population

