4.1 Inclusion Criteria

The subject will not be considered eligible for the study without meeting all of the criteria below.

1. Be ≥ 12 years of age, or in Germany and Israel, be ≥ 18 years of age.
2. Have a diagnosis of HAE (Type I or II) and a functional C1 INH level less than 50% of normal.
3. Meet one of the following criteria (attack rate may be based on subject recall in conjunction with the subject's medical records):
 - If subject is adult (≥ 18 years of age) and currently receiving prophylactic therapy with C1 INH, have a history of ≥ 2.0 angioedema attacks per month (average) during the 3 consecutive months prior to starting prevention therapy.

OR

- If subject is adolescent (≥ 12 and < 18 years of age) or adult and not receiving prophylactic therapy with C1 INH, have a history of ≥ 2.0 angioedema attacks per month (average) during the 3 consecutive months prior to the screening visit.

OR

- If subject is adult (> 18 years of age) and currently receiving a stable dose of attenuated androgens, have a history of ≥ 2.0 angioedema attacks per month (average) during the 3 consecutive months prior to the screening visit.

4. For subjects ≥ 18 years of age, be willing to receive treatment with icatibant for any angioedema attacks that occur during the study that, in the opinion of the healthcare care provider, require medical intervention. Note: For subjects ≥ 12 to < 18 years of age, standard of care therapy per local protocols should be provided.

5. Agree to adhere to the protocol-defined schedule of assessments.
6. If female, must have a negative serum beta human chorionic gonadotrophin (β -hCG) pregnancy test at the screening visit and must have a negative urine pregnancy test prior to the first dose of investigational product (Visit 1a), and agree to comply with any applicable contraceptive requirements of the protocol.
7. If male, be surgically sterile or agree to follow an acceptable method of birth control (eg, abstinence, barrier control) from the screening visit through 2 months after the last dose of investigational product.
8. If an adult (≥ 18 years of age), be informed of the nature of the study and provide written informed consent before any study-specific procedures.

OR

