5.2.2 Prohibited Treatment

Use of C1 INH therapy (other than investigational product) for prophylaxis against angioedema attacks is prohibited during this study (from the first dose of investigational product through the 1-month post-treatment visit).

The initiation of androgen therapy is prohibited during the study (from the first dose of investigational product through the 1-month post-treatment visit).

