7.2.3.1 Medical and Medication History

A medical history will be taken at the screening visit. All medical history findings that have been present/active within the 5 years prior to enrollment will be entered into the CRF regardless of clinical relevance or presence at study start. Medical history findings that have not been present within the 5 years prior to enrollment will be recorded if deemed clinically relevant by the investigator to the conduct of the study. The medical history should include any history of allergic reactions to drugs.

HAE History

The following information associated with HAE history will be recorded in the CRF at the screening visit. If there is no documented C1 INH antigen level and/or C1 INH functional activity in the subject's medical record, a blood sample can be collected at screening and sent to a local or central laboratory (as appropriate) to confirm HAE diagnosis (Type I or II). Repeat blood sampling is allowed if the test is non-confirmatory despite a suspected diagnosis of HAE. (Note: the attack rate may be estimated based on subject or parent/caregiver recall as well as the subject's medical records):

- HAE type (I or II)
- Estimated date of last angioedema (swelling) attack prior to the screening visit
- Any therapy received during the last 12 months for management of HAE (Section [5.1](#))
- Total number, typical locations and average overall duration (days), and average overall severity of angioedema attacks experienced:
 - during the 3 consecutive months prior to the screening visit (all subjects)
and (if applicable)
 - during the 3 consecutive months prior to starting prophylactic therapy with C1 INH or androgens.
- Typical score, estimated on a scale from 0-100, for the subject's angioedema attack pain:
 - during the 3 consecutive months prior to the screening visit (all subjects)
and (if applicable)
 - during the 3 consecutive months prior to starting prophylactic therapy with C1 INH or androgens.

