9.8.2.2 Other Secondary Efficacy Endpoints

Other secondary efficacy endpoints to be evaluated in this study are:

- To determine the proportions of subjects achieving at least a 50% reduction in the NNA during a treatment period relative to the pretreatment assessment.
- Cumulative attack severity. This score is the sum of the maximum symptom severity recorded for each angioedema attack in a treatment period.

- Cumulative daily severity. This score is the sum of the severity scores recorded for every day of reported symptoms in a treatment period.
- Number of attack-free days during a treatment period.
- Number of angioedema attacks requiring acute treatment a treatment period.
- Disease activity as measured by the 98-day AAS. This score is the sum of the daily AAS during a treatment period, where the daily AAS is the sum of AAS items per day.
- Results of the AE-QoL questionnaire.
- Determine the response to icatibant when administered as treatment for an acute angioedema attack by:
 - Time to subject-assessed initial symptom improvement (TISI)
 - Time to subject-assessed complete symptom resolution (TCSR)

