3.2 Secondary Objectives

The key secondary objectives are to demonstrate the superior efficacy of SC administration of 2000 IU C1 esterase inhibitor [human] liquid for injection for the prevention of angioedema attacks relative to placebo as measured by:

- 1. The proportion of subjects meeting the criterion of at least 50% reduction in the NNA during the 2000 IU C1 esterase inhibitor [human] liquid for injection treatment period relative to the placebo perio
- 2. The NNA during each treatment period excluding the first 2 weeks
- 3. The proportion of subjects meeting the criterion of at least a 50% reduction in the NNA for the 2000 IU C1 esterase inhibitor [human] liquid for injection treatment period relative to the placebo period excluding the first 2 weeks of each treatment period.

Other secondary objectives are:

- To assess the proportion of responders during treatment with 2000 IU C1 esterase inhibitor [human] liquid for injection relative to treatment with placebo, where the proportion of responders is defined as achieving at least a 50% reduction, and/or achieving reduction to less than 1 NNA during a treatment period relative to the pretreatment assessment (ie, the subject's attack rate without prophylactic treatment)
- To assess the severity of angioedema attacks during treatment with 2000 IU C1 esterase inhibitor [human] liquid for injection relative to treatment with placebo
- To assess the number of attack-free days during treatment with 2000 IU C1 esterase inhibitor [human] liquid for injection relative to treatment with placebo
- To assess the number of angioedema attacks requiring acute treatment during treatment with 2000 IU C1 esterase inhibitor [human] liquid for injection relative to treatment with placebo
- To assess the safety and tolerability of SC administration of 2000 IU C1 esterase inhibitor [human] liquid for injection
- To assess the immunogenicity of SC administration of 2000 IU C1 esterase inhibitor [human] liquid for injection

CONFIDENTIAL

- To characterize the PK and PD of SC administration of 2000 IU C1 esterase inhibitor [human] liquid for injection
- To assess the clinical response and safety/tolerability of icatibant (Firazyr[®]) for the treatment of acute angioedema attacks (applicable for subjects ≥ 18 years of age)
- To assess disease activity as measured by the Angioedema Activity Score (AAS)

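### The pretreatment responder endpoint scores subjects who stay on androgens against their attack rate before androgens, which inflates their response on both treatments

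*Protocol*

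**What the plan says.** **Reference rate.** Protocol 9.8.2.2 states the endpoint as "To determine the proportions of subjects achieving at least a 50% reduction in the NNA during a treatment period relative to the pretreatment assessment". Neither that section nor SAP 10.4 says what the pretreatment assessment is. The only definition is a parenthesis in the objective. Protocol 2.2.2 has "relative to the pretreatment assessment (ie, the subject's attack rate without prophylactic treatment", and SAP 3.2 repeats it: "ie, the subject's attack rate without prophylactic treatment". SAP 10.4 adds cuts at 70%, 90% and 100% reduction and at fewer than 1 attack per month. The derivations in SAP 19.1 and 19.2 do not cover this endpoint.

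**Who is on androgens.** The third option of inclusion criterion 3 (Protocol 4.1) admits adults "currently receiving a stable dose of attenuated androgens, have a history of" at least 2.0 attacks per month in the 3 months before screening. Their qualifying rate is thus measured on androgens. SAP 12.5.6 plans an oral androgen subgroup at randomization, so such subjects are expected.

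**What happens on study.** Protocol 5.2.2 treats the two kinds of prophylaxis differently. For C1 INH: "Use of C1 INH therapy (other than investigational product) for prophylaxis against angioedema attacks is prohibited during this study". For androgens: "The initiation of androgen therapy is prohibited during the study (from the first dose of investigational product through the 1-month post-treatment visit". SAP 19.4 item 23 likewise makes only the initiation of long-term therapy a major deviation.

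**What is recorded.** Protocol 7.2.3.1 collects the attack history for the 3 months before screening in all subjects and, where applicable, "during the 3 consecutive months prior to starting prophylactic therapy with C1 INH or androgens". Androgens are therefore counted as prophylaxis, and two candidate reference rates exist for an androgen user.

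**Test.** McNemar's test compares responder proportions between the active and placebo periods (Protocol 9.8.2.2, SAP 10.4).

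**The concern.** A reference rate should reflect the background therapy the subject has during the period being scored. For C1 INH users it does: they come off prophylaxis, so a rate without prophylaxis fits. For subjects who continue androgens it does not. Their NNA is measured on androgens in both periods and compared with a rate from before androgens were started, possibly long ago.

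Whatever the androgen had already achieved is then scored as response to the study treatment, whether that is active or placebo. The endpoint is meant to describe response to 2000 IU relative to placebo and gives a percentage that is easy to quote on its own. For these subjects it partly measures androgen response.

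**Working it through.** The plan gives no expected rate, power or sample size for this endpoint, so there is no figure of its own to reproduce. What follows is an illustration.

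**Inputs from the documents**
- NNA = 30.4 × attacks / days (Protocol 9.8.1); a full period is 14 × 7 = 98 days.
- Response means NNA ≤ 0.5 × reference rate, the 50% cut.
- Minimum qualifying rate 2.0 per month; 52 crossover subjects (26 + 26).

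**Assumptions not in the documents**
- Attack counts are Poisson, with no placebo effect and a complete period.
- Two example subjects: A, 4 per month before androgens and 2 on them; B, 6 before and 2.5 on them.
- Androgen users are 10-20% of crossover subjects (about 5-10 of 52).

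**Formula.** For reference R and true rate r, the chance of response is P(X ≤ k), where X is Poisson with mean r × 98/30.4 and k is the whole-number part of 0.5 × R × 98/30.4.

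**Placebo period, 50% cut**

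| Subject | Mean count | Reference | 0.5 × R × 98/30.4 | k | Chance of response |
|---|---|---|---|---|---|
| A | 6.45 | 4 (as defined) | 6.45 | 6 | 53.5% |
| A | 6.45 | 2 (on androgens) | 3.22 | 3 | 11.6% |
| B | 8.06 | 6 (as defined) | 9.67 | 9 | 70.9% |
| B | 8.06 | 2.5 (on androgens) | 4.03 | 4 | 9.6% |

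Ignoring random variation, B shows a reduction of (6 − 2.5)/6 = 58% on placebo as defined, and 0% against the on-androgen rate.

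**Effect on the overall placebo responder rate** (share × difference)
- A: 0.10 × 41.9 = 4.2 points; 0.20 × 41.9 = 8.4 points.
- B: 0.10 × 61.3 = 6.1 points; 0.20 × 61.3 = 12.3 points.

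**Active period**, if the drug halves the on-androgen rate. A responds with probability 95.4% as defined against 59.7% with the matched reference. The active-minus-placebo difference is 95.4 − 53.5 = 42 points as defined and 59.7 − 11.6 = 48 matched. For B the difference is 28 points as defined and 53 matched.

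**Does the contrast always shrink?** With 2 attacks per month on androgens, the active-minus-placebo difference in points, as defined, is:

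| Androgen benefit | 0% | 25% | 40% | 50% |
|---|---|---|---|---|
| Drug halves the rate | 48 | 55 | 52 | 42 |
| Drug cuts the rate by 70% | 75 | 72 | 61 | 46 |

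The 0% column equals the matched-reference result. With a halving drug, the contrast is larger than matched at moderate androgen benefit and falls below it only at about 50%.

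**Other cuts, subject A on placebo**
- 70%: 0.3 × 4 × 98/30.4 = 3.87, k = 3, chance 11.6%; matched 1.93, k = 1, chance 1.2%.
- 90%: 0.1 × 4 × 98/30.4 = 1.29, k = 1, chance 1.2%; matched 0.64, k = 0, chance 0.2%.
- 100%: zero attacks, whatever the reference.
- Fewer than 1 per month: an absolute level. In these examples both candidate references exceed 1, so the choice between them does not matter.

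**The case against.** **The reference is a stated choice.** The objective openly names untreated disease as the comparator, and placebo is held to the same standard. That is fair, and it is why the McNemar comparison is not systematically tilted toward active treatment. It does not help the absolute responder percentages, which are still read as response to the assigned treatment.

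**The consequence is limited.** This stands. The endpoint lies outside the testing hierarchy, and trial success rests on the primary endpoint alone. The primary endpoint and key secondaries 1 to 3 compare active with placebo periods, so a stable background androgen is common to both sides. Key secondary 1 already answers the 50% question with a matched comparator.

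**The SAP might use the pre-screening rate anyway.** If so, the problem disappears, but nothing says so, and it would contradict the only definition given.

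**Continued use is an inference.** No sentence expressly permits it. It follows from eligibility on a stable dose, a prohibition confined to initiation, and the absence of any requirement to stop.

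A reader might go further and infer that androgen responders can never be discordant in McNemar's test. They can. If the two periods are independent, subject A is discordant with probability 0.954 × 0.465 + 0.046 × 0.535 = 47%, and subject B about 29%. A reader might also infer that every SAP cut is affected, or that the treatment difference must be diluted. The working shows neither holds.

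**Conclusion.** The mismatch is real on the text. Followed as written, the plan inflates responder rates on both treatments for subjects who continue androgens, at the 50%, 70% and 90% cuts. In the two examples, placebo response at the 50% cut is 53.5% instead of 11.6%, and 71% instead of 10%. Overall that is roughly 4-12 points, resting on the assumed 10-20% share, Poisson counts and no placebo effect. A rise of the full 10-20 points would require every androgen user to move from certain non-response to certain response on placebo, which the model does not support.

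Dilution of the treatment contrast is possible and becomes clear when androgen benefit is about 50% or more. Below that, its direction depends on the drug effect. The point deserves correction before unblinding because the remedy is a rule for choosing between recorded rates. It does not threaten the trial's main conclusions.

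**What to change.** In Protocol 9.8.2.2 and SAP 10.4, define the pretreatment rate by subject:

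- **Not on C1 INH prophylaxis at entry**, including those continuing androgens or other oral prophylaxis: the 3 months before screening.
- **Stopping C1 INH prophylaxis at entry**: the 3 months before C1 INH was started.

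This mirrors inclusion criterion 3. Reword the parenthesis in Protocol 2.2.2 and SAP 3.2 to match. Also state which recorded rate applies to anyone on both C1 INH and androgens, because the history item refers to the start of either therapy and does not say which one counts.

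The rule also covers users of other oral prevention (a category in SAP 12.5.6), for whom Protocol 7.2.3.1 does not ask for a rate before that therapy.

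The cost is a short definition, with no new data collection apart from settling the case of combined use. Treatment rules do not change. Reported responder rates on both treatments will be somewhat less favourable.
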